4.4.3 Further binary endpoints

The other pre-specified binary endpoints, i. e. achievement of EASI 100 response and achievement of $a \ge 3$ point improvement (reduction) in the weekly average of the Peak Pruritus 0-10 NRS from baseline at Week 12 (Day 84) will be analyzed similar to the primary endpoint.

4.4.4 Descriptive statistics for binary efficacy endpoints for all time points

The number and frequency of participants with EASI 75 response will be summarized

- for each scenario described in Section 4.2 (refer to Table 4-1) (denominator = number of all participants in analysis set due to imputation of all missing values),
- for the raw data including all values as recorded (denominator = number of participants in analysis set per visit),
- for raw data after setting all values after use of rescue medication at Day 56 (Visit 6) or later and after use of SoC to missing (denominator = number of participants in analysis set per visit),
- for raw data after setting all values after use of rescue medication at Day 1 (Visit 3) or later and after use of SoC to missing (denominator = number of participants in analysis set per visit).

If EASI 75 response will be imputed using logistic regression, several (potentially different) EASI 75 responses will be available per participant. In this case the responses of the participant will be averaged over all imputed data sets. The average will be used to count the number and frequency of participants with EASI 75 response (i. e. non-integer numbers of EASI 75 responders are possible to summarize frequencies most accurately).

All other binary endpoints will be summarized similarly.

In addition, the number and frequency of participants with vIGA-AD scores (0, 1, 2, 3, 4) will be summarized (the three summaries based on raw data as described above, no imputation will be performed for vIGA-AD values).

4.4.5 Descriptive statistics for continuous efficacy endpoints for all time points

Summary statistics will be presented for EASI scores including percent change and absolute change from baseline.

- for imputed data after each type of imputing as outlined above (refer to table in Section 4.3.2),
- for raw data including all values as recorded,
- for raw data after setting all values after use of rescue medication at Day 56 (Visit 6) or later and after use of SoC to missing,
- for raw data after setting all values after use of rescue medication at Day 1 (Visit 3) or later and after use of SoC to missing.

If EASI scores will be imputed using linear regression, several different EASI scores will be available per participant. In this case the scores of the participant will be averaged over all imputed data sets. The average will be used for calculation of summary statistics.

The summary statistics for raw data will also comprise changes from end of treatment to follow-up.

For imputed data after each type of imputing (refer to table in Section 4.3.2) the following outputs will be presented as well:

Histograms will be presented together with a box-plot for percent change from baseline in EASI score at Day 84 (Visit 7) by treatment group (in one plot).

In addition, a frequency table will be presented for the main analysis summarizing percent change in EASI from baseline at Day 84 (Visit 7) by -100% to -90%, >-90 to -80%, >-80 to -70%, ..., >-20 to 10%, >-10 to <0%, 0 to 10%, >10% to 20% etc. including cumulative frequencies.

Individual plots of EASI scores (raw data including all values as measured) will be presented as well based on the FAS. EASI scores after systemic SoC use or use of rescue medication at or after Day 56 (Visit 6) will be marked.

Similar outputs will be presented for weekly average of Peak Pruritus 0-10 NRS and BSA affected by AD (BSA with absolute changes and change categories of 5% steps for frequencies).

In addition, mean plots over time of daily Peak Pruritus 0-10 NRS score will be presented (similar to the three summaries based on raw data as described above, no imputation will be performed for daily peak pruritus values).

Relations between endpoints

Relations between outcome variables will be analyzed on the PPS after imputing according to model $C_{1.1} + B_{1.1}$ (refer to Section 4.3.2 and 4.2.4). To examine the relationship between the response variables with respect to treatment effect at Day 84 (Visit 7) a spiderweb will be presented by treatment group displaying the following values on the axes of the web:

- mean percent change in EASI score from baseline,
- mean percent change in weekly average of Peak Pruritus 0-10 NRS from baseline,
- mean absolute change in BSA affected by AD from baseline,
- frequency of achievement of a vIGA-AD response (score 0 or 1 and ≥ 2 points improvement),
- frequency of achievement of 75% reduction from baseline in the Eczema Area and Severity Index (EASI 75 response),
- frequency of achievement of $a \ge 4$ point-improvement (reduction) in the weekly average of the Peak Pruritus 0-10 NRS score from baseline.

The mean values will be normalized with respect to 99th percentile minus 1st percentile. The frequencies will be presented on an axis from 0 to 1. The mean changes and frequencies at Day 84 (Visit 7) will be connected by lines. The points on the axes reflecting no change (zero) or a frequency of 0% will be presented and connected by lines as well.

Scatter plots including Pearson and Spearman correlation coefficients will be presented on the PPS after imputing according to model C_1.1 for:

- absolute change in EASI at Day 84 (Visit 7) from baseline versus absolute change in BSA affected by AD at Day 84 (Visit 7) from baseline,
- absolute change in EASI at Day 84 (Visit 7) from baseline versus absolute change in weekly average of Peak Pruritus 0-10 NRS at Day 84 (Visit 7) from baseline,
- absolute change in BSA affected by AD at Day 84 (Visit 7) from baseline versus absolute change in weekly average of Peak Pruritus 0-10 NRS at Day 84 (Visit 7) from baseline.

The three scatter plots above will also be presented showing percent change from baseline for both respective variables.

Furthermore, individual plots will be presented on the SAF with the time course of absolute EASI score, absolute weekly average of Peak Pruritus 0-10 NRS, absolute BSA affected by AD, and vIGA-AD in one plot per participant. Raw data will be presented. Use of systemic SoC and use of rescue medication (at any time) will be presented as boxes from start to end of use. Date of discontinuation of study intervention will also be indicated (in case of early

discontinuation of study intervention differing by early discontinuation due to lack of efficacy or other reasons). The study day will be presented on the x-axis. Participant identifier and validity for analysis sets will be indicated above each plot as PPS (if in PPS), FAS (if in FAS and not PPS) or SAF (if not in PPS and not in FAS).

Influence of baseline characteristics

The influence of baseline characteristics will be analyzed on the PPS after imputing according to model C_1.1 (see Section 4.3.2, the scores derived from multiple imputation for each participant will be averaged over all imputed data sets for this analysis). To identify the most influential set of baseline characteristics explaining the change in the EASI score at Day 84 (Visit 7) regression analyses will be performed with percent change in EASI score from baseline at Day 84 (Visit 7) as dependent variable and treatment and the following baseline characteristics as predictors:

- treatment (zabedosertib or placebo),
- age,
- body mass index (BMI) at baseline,
- sex,
- race (only if at least two categories with at least n=5 per treatment group),
- EASI at baseline,
- BSA affected by AD at baseline,
- vIGA-AD at baseline,
- weekly average of Peak Pruritus 0-10 NRS at baseline,
- disease duration at baseline,
- age of onset,
- number of AD flares in the year before informed consent,
- history of asthma, allergic rhinitis or allergic conjunctivitis (yes/no),
- IgE level at baseline
- previous treatment with systemic standard of care for AD within 6 months (i. e. 183 days) before start of study drug (yes/no)
 (refer to Section 6.3 for a list with respective medication).

Univariate regression with only one variable per regression model will be performed and a multiple regression model will be applied using 'forward selection'. This stepwise procedure starts with no explanatory variables in the model, then testing the explanatory variables one by one in univariate models. The most significant variable will be added to the model given the p-value is below a certain threshold (≤ 0.2). Then all variables will be added one by one to the current model and the most significant one will be added if the p-value is ≤ 0.2 . This step will be iterated until no further variables can be added to the model, i. e. p>0.2 for all remaining variables.

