In a first step any values (set to) missing after rescue medication use at or after Day 56 (Visit 6), i.e until Day 84 (Visit 7) or end of treatment if before Day 84 (Visit 7), after use of systemic SoC and after discontinuation of study intervention due to lack of efficacy will be imputed by carrying forward the worst observed post-dose value to impute the value at Day 84 (Visit 7) (refer to Section 8.4.3). SoC medication use after early discontinuation due to other reasons will not trigger the imputation by worst observed post-dose value carried forward for the following time points.

The remaining missing values at Day 84 (Visit 7) will be imputed using a multiple imputation procedure based on the absolute values of the EASI score.

The imputation will be performed by treatment group using the monotone linear regression method from the SAS multiple imputation procedure (PROC MI).

For a participant

- with EASI score at baseline and Day 56 (Visit 6),
- without EASI score at Day 84 (Visit 7),
- without systemic SoC use before Day 56 (Visit 6) EASI score,
- without rescue medication use at Day 56 (Visit 6) EASI score

a linear regression model will be built based on the following participants:

- with EASI score at baseline and Day 56 (Visit 6),
- with EASI score at Day 84 (Visit 7),
- without systemic SoC use before Day 56 (Visit 6) EASI score,
- without rescue medication use at Day 56 (Visit 6) EASI score,
- without rescue medication use (irrespectively of the indication) within the 7 days before the Day 56 (Visit 6) EASI score (to avoid influence of EASI scores directly after rescue medication on the imputation of the value at Day 84 (Visit 7)).

Participants with use of systemic SoC or rescue medication or discontinuation of study intervention due to lack of efficacy after the Day 56 (Visit 6) EASI score and until Day 84 (Visit 7) will have an EASI score (worst post dose observation) at Day 84 (Visit 7) and can be included in the linear regression model if they fulfill the criteria specified above.

The EASI score at Day 84 (Visit 7) will be the dependent variable in the linear regression model and the following variables will be included as independent variables:

- EASI score at baseline,
- EASI score at Day 56 (Visit 6).

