If the multiple imputation using linear regression as described above is based on less than 8 participants per treatment group the baseline EASI score and the EASI score at the previous visit will be used as independent variable in the linear regression model as described above. If there will not be sufficient participants to include one of the post-dose visits (Day 28 (Visit 5),

or – if not possible – Day 14 (Visit 4)) the linear regression model will only use the EASI score at baseline as independent variable. Then the model will be based on all participants with EASI score at baseline and EASI score at Day 84 (Visit 7). The EASI at Day 84 (Visit 7) could be imputed using worst post-dose observation carried forward after SoC use, discontinuation of study intervention due to lack of efficacy or use of rescue medication after Day 56 (Visit 6). The variables used in the regression model will be indicated below the output table.

If there is a participant with rescue medication use within the 7 days before the Day 56 (Visit 6) EASI score and missing EASI at Day 84 (Visit 7) which needs to be imputed the same procedure as described above (in case of less than 8 participants per treatment group) will be applied for that participant.

Imputed values below the minimum (0) or above the maximum (72) possible EASI score will be set to the minimum or maximum score.

Imputation according to the procedure defined above will be performed 50 times. All participants with EASI scores imputed using the linear regression method will be combined with the remaining participants (which will have the same values for each imputed dataset).

Then an analysis of covariance (ANCOVA) with the percent change from baseline in the EASI score at Day 84 (Visit 7) as dependent variable will be applied for each imputed dataset. The model will include treatment group as fixed effect and the EASI baseline value as covariate. The results from the model will be combined by Rubin's rule using SAS MIANALYZE procedure. The treatment difference (including 95% confidence intervals) at Day 84 (Visit 7) will be presented.

As a "worst case" scenario the analysis will be repeated by imputing all missing EASI scores at Day 84 (Visit 7) by carrying forward the worst post-dose EASI score (refer to Section 8.4.3 for details).

Furthermore, the analysis will be repeated by imputing all missing EASI scores at Day 84 (Visit 7) using last observation carried forward (refer to Section 8.4.3 for details).

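### Averaging the multiply imputed scores per participant understates the SDs in the summary tables and the treatment standard error in the exploratory baseline-characteristics regression (SAP 4.4.5)

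*SAP*

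**What the plan says.** SAP 4.3.2 sets out the main analysis of percent change in EASI at Day 84 (C_1.1). A Day 84 value that is missing, or set to missing, after rescue at or after Day 56, systemic standard of care or a stop for lack of efficacy is "imputed by carrying forward the worst observed post-dose value". The remaining missing values are multiply imputed from baseline and Day 56 EASI. "The imputation will be performed by treatment group using the monotone linear regression method", and "Imputation according to the procedure defined above will be performed 50 times". An ANCOVA is fitted to each data set, and "The results from the model will be combined by Rubin's rule using SAS MIANALYZE procedure".

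SAP 4.4.5 then uses imputed scores in two other ways:

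- **Summary statistics.** Each participant's imputed scores are averaged over the imputations. "The average will be used for calculation of summary statistics". This applies to every imputation type in Table 4-2, and so to the four that use linear-regression imputation: C_1.1, C_2.4, C_3.4 and C_5.4.
- **Influence of baseline characteristics** (PPS, C_1.1 only). Here "the scores derived from multiple imputation for each participant will be averaged over all imputed data sets for this analysis". The average is the outcome in univariate regressions and in a forward selection over 15 candidate predictors, treatment among them. "The most significant variable will be added to the model given the p-value is below a certain threshold" of 0.2, and the step is repeated.

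SAP 4.4.4 treats binary endpoints in the same way: "In this case the responses of the participant will be averaged over all imputed data sets".

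**The concern.** Multiple imputation draws each missing value with residual noise and with uncertainty in the imputation model, so that later analyses do not treat a guess as a measurement. Averaging the draws first removes both components. The averaged score lies close to the regression line, and SAP 4.4.5 then gives it the same weight as an observed score. The same C_1.1 data therefore receive two incompatible treatments of uncertainty: pooling in the ANCOVA of 4.3.2 and none in 4.4.5.

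At stake are the SDs printed in the imputed-data tables and the entry of treatment into a selection procedure that runs on p-values. The frequencies in 4.4.4 are not at stake. The mean of averaged responses equals the average of the per-imputation proportions, so the reported percentage is correct, and the same holds for the means in 4.4.5.

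**Working it through.** The SAP states no figure on this point, so there is none to reproduce. The evaluable numbers, 38 and 19 (57 in total), come from SAP Section 5. All other inputs below are assumptions.

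**1. SD in the summary tables.** Let f be the fraction of participants multiply imputed and R² the share of variance that the imputation model explains. Take the outcome variance as 1, with the same mean in observed and imputed participants. Observed scores have variance 1 and averaged scores about R², so

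SD ratio = √[(1 − f) + f·R²].

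Example: f = 0.10 and R² = 0.3 give √(0.90 + 0.03) = √0.93 = 0.964, an SD 3.6% too low.

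| f | R² = 0.3 | R² = 0.5 | R² = 0.7 |
|---|---|---|---|
| 5% | 0.982 (−1.8%) | 0.987 (−1.3%) | 0.992 (−0.8%) |
| 10% | 0.964 (−3.6%) | 0.975 (−2.5%) | 0.985 (−1.5%) |
| 20% | 0.927 (−7.3%) | 0.949 (−5.1%) | 0.970 (−3.0%) |
| 40% | 0.849 (−15.1%) | 0.894 (−10.6%) | 0.938 (−6.2%) |

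**2. Treatment in the regression.** The C_1.1 imputation was simulated with 38 and 19 participants, imputation by arm from baseline and Day 56 EASI, 50 imputations, and values limited to 0–72. Assumed: SD of percent change 35 points, and correlation between Day 56 and Day 84 of 0.5, 0.7 or 0.85. Percent change was regressed on treatment, baseline EASI and one covariate outside the imputation model. There were 4000 runs per null scenario. Ranges are over the three correlations.

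| Imputed of 57 | SD, averaged / proper | Treatment SE, averaged / Rubin | Null rejection at 0.05, averaged | Null rejection at 0.20, averaged |
|---|---|---|---|---|
| 3 | 0.97–0.99 | 0.95–0.98 | 0.05–0.06 | 0.20–0.22 |
| 6 | 0.95–0.98 | 0.89–0.95 | 0.06–0.07 | 0.21–0.25 |
| 12 | 0.89–0.96 | 0.79–0.90 | 0.07–0.10 | 0.22–0.29 |

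With Rubin pooling, null rejection was 0.04–0.05 and 0.18–0.20. The simulation standard error is about √(0.05 × 0.95/4000) = 0.003 at the 0.05 level and √(0.2 × 0.8/4000) = 0.006 at the 0.20 level. The inflation is therefore barely visible with 3 imputed and clear from about 6. The simulated SD shortfall at 12 of 57 is somewhat larger than the formula gives at 20%. A likely reason is that proper draws also carry uncertainty in the imputation coefficients, which the formula leaves out.

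**3. A covariate outside the imputation model.** Under the null, averaging rejected at 0.04–0.06 (nominal 0.05) and 0.18–0.20 (nominal 0.20), so the error rate is nominal. With a real effect (6 imputed, correlation 0.7, 3000 runs) the coefficient was 8.4 against 9.5 on complete data. That is a loss of 1 − 8.4/9.5 = 12%, close to the imputed share 6/57 = 11%. The median p-value rose to 0.066 from 0.042.

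**4. Which outputs are reached.** The regressions use C_1.1 alone. For C_2.4, C_3.4 and C_5.4 the averaging enters only the descriptive summaries, because SAP 4.4.2 refers their inference back to the ANCOVA that 4.3.2 pools. The primary analysis (4.2.2) combines posterior samples over all imputed data sets.

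**The case against.** The best case for leaving the plan alone is that little is touched and nothing is decided on it. In C_1.1 few participants should need multiple imputation:

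- The PPS requires an EASI score at Day 56 or later unless there is a failure event.
- Failure events receive a single worst value.
- Valid scores from Day 76 to Day 92 count as Day 84 (Table 8-3).
- The imputation model includes the same participant's EASI four weeks earlier, so R² may well exceed 0.3.

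The summary tables also appear beside three raw-data versions, the selection is exploratory, and SAP 2.1 declares the whole study exploratory. All of this stands. It keeps the point minor but does not make the averaged SD or the treatment standard error correct.

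A reader might infer that every p-value in the selection is too small. The check does not support that. Inflation was shown for treatment, which enters the imputation because imputation is by arm. Baseline EASI is also in the imputation model, but its p-value was not examined. For predictors outside that model, such as age, sex, BMI or IgE, the null error was nominal and a real effect was diluted.

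A reader might also infer that p-values in C_2.4 and C_5.4 are affected, since most imputation is likely there. They are not, because that inference is pooled. Whether treatment and baseline EASI should be forced into every model is a separate preference. The adjusted treatment effect already comes from the ANCOVA, which contains both.

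**Conclusion.** The point holds in a limited form. The averaging in SAP 4.4.5 understates the SDs of the outputs imputed by linear regression, and it understates the treatment standard error and p-value in the C_1.1 baseline-characteristics regression. For predictors outside the imputation model, the consequence is attenuation.

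For C_1.1, with 5–10% imputed and R² of 0.3 to 0.7, the SD is low by about 1–4%. Shortfalls of 3–7% (20% imputed) or 6–15% (40% imputed) are plausible only for the descriptive SDs of C_2.4 and C_5.4, where every value after any rescue use is imputed, and only if rescue is frequent. The SAP itself expects scarce rescue-free data (4.2.4, 4.4.2) but gives no figure. The 40% row rests on the formula alone and was not simulated. No conclusion from the primary endpoint or the ANCOVAs changes.

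**What to change.** - **Summary tables.** Report the mean over imputations, and the SD as the square root of the average within-imputation variance. State the number multiply imputed per arm.
- **Baseline-characteristics regressions.** Fit the univariate and forward-selection models in each of the 50 data sets and pool by Rubin's rule with PROC MIANALYZE, as in 4.3.2. State the selection rule: at each step, enter the predictor with the smallest pooled p-value if it is at most 0.2.
- **Predictors absent from the imputation model.** Label their p-values as descriptive. Pooling alone does not remove the attenuation, and in the simulation it was conservative for such a covariate (null rejection 0.11–0.19 at nominal 0.20).

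The cost is modest extra programming, mostly for the pooled selection step, and slightly wider SDs and standard errors.

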Investigators should make every attempt to conduct efficacy and safety assessments immediately before administering any AD treatment prohibited in the study (see Section 6.9.3) or rescue medication (see Section 6.9.2). An unscheduled visit may be used for this purpose, if necessary.

Screening (population characteristics)

Demography

Subject to local legislation, the following information will be collected for demography in the eCRF: Year of birth, age, sex, ethnicity and race.

Medical history and AD history

All relevant information on medical history including history of COVID infection(s), history of AD and associated comorbidities will be collected in the eCRF at screening.

History of AD will include: Date of AD diagnosis, number of AD flares and episodes of skin infections requiring pharmacological treatment within the last year prior to screening, history of asthma, allergic rhinitis and allergic conjunctivitis.

Any SARS-CoV-2 vaccination prior to study entry should be recorded independent of the timeframe under prior/concomitant medication.

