For analytes which are below the lower limit of quantification (LLOQ), one half of the LLOQ will be used as an estimate for the respective value. However, means, standard deviations and coefficients of variation will only be calculated if at least 2/3 of the values are above (or equal to) the LLOQ. In tables showing mean values, where values below LLOQ are included in the calculation of mean values, these means will be marked. Corresponding tables and figures will get a footnote indicating that "Values below the lower limit of quantification were replaced by $\frac{1}{2}$ LLOQ if at least 2/3 of the values were >= LLOQ." Tables displaying minimum values will present "<LLOQ" as minimum. Similar rules will apply to data points above ULOQ. ULOQ will be used as an estimate for the respective values. Means, standard deviations and coefficients of variation for changes to baseline will only be calculated if there are at least 2/3 of the changes where the baseline and post-dose value are >= LLOQ and <=ULOQ.

The relative onset of adverse events with respect to treatment start will be expressed in days as follows (similar for relative end of adverse events):

- date of adverse event start minus date of treatment start for adverse events starting before treatment start
- date of adverse event start minus date of treatment start + 1 for adverse events starting on day of first treatment or later.

The duration of an AE will be calculated in days, i. e., the date of adverse event end minus the date of adverse event start +1.

The relative onset of prior/concomitant/posterior medication with respect to treatment start will be expressed in days as follows (similar for relative end of prior/concomitant/posterior medication):

- date of medication start minus date of treatment start for medications starting before treatment start
- date of medication start minus date of treatment start + 1 for medications starting on day of treatment start or later.

The duration of atopic dermatitis (in years) at baseline will be calculated as follows:

• (date of Day 1 (Visit 3) minus date of first diagnosis plus 1) / 365.25.

The age at onset (in years) will be calculated as follows:

• year of AD onset – year of birth.

Data from unscheduled measurements will be listed, but not included in summary statistics or frequency tables by visit unless specified otherwise (refer to Section 8.4 for handling of unscheduled measurements for efficacy variables).

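### Forward selection at p ≤ 0.2 from 14–15 candidates is expected to admit about three factors by chance and does not guarantee treatment a place, so the selected set cannot be read as most influential on its own

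*SAP*

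**What the plan says.** SAP 4.4.5, under the sub-heading on the influence of baseline characteristics, states the purpose: "To identify the most influential set of baseline characteristics explaining the change in the EASI score at Day 84 (Visit 7"). The outcome is percent change in EASI on the PPS, imputed as in analysis C_1.1 and averaged over the imputed data sets.

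The candidate list has 15 entries: "treatment (zabedosertib or placebo") and 14 baseline characteristics. Race counts only if at least two categories have five or more participants per arm, so the total may be 14. Each candidate is first fitted alone, and then a multiple model is built. On that model the SAP says "This stepwise procedure starts with no explanatory variables in the model", and that the best candidate is added "given the p-value is below a certain threshold (≤ 0.2"). This repeats until nothing qualifies. There is no removal step, no variable is named as forced in, and no validation, shrinkage or stability check is described.

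Age, disease duration and age of onset are all on the list. SAP 4.1.1 defines duration as ("date of Day 1 (Visit 3) minus date of first diagnosis plus 1) / 365.25" and age of onset as "year of AD onset – year of birth". Protocol 8.1 says "History of AD will include: Date of AD diagnosis", followed by flares, skin infections and atopic comorbidities; it lists no separate onset date.

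SAP 5 plans 57 evaluable participants (38 zabedosertib, 19 placebo). SAP 2.1 makes no multiplicity adjustment because the study is exploratory.

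**The concern.** The stated aim is identification of a set of factors. The rule used tests many candidates at a lenient threshold, with about four participants per candidate (57/15 = 3.8; 57/14 = 4.1). Such a rule returns a list whether or not any factor matters, and the output as planned gives a reader no means of telling the two cases apart.

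Two features add to this. First, the randomised arm is treated like any other candidate. The univariate models contain one variable each, so they exclude treatment by construction, and the multiple model may exclude it too. The SAP's ANCOVA (4.3.2) and repeated-measures model (4.4.2) always contain treatment. Second, three time variables that nearly determine one another compete for entry, so which one is named can depend on rounding and chance.

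At stake is the interpretation of an exploratory table: whether the named factors can be called influential.

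**Working it through.** **1. The plan's own figure.** The documents give no operating figure for this regression. Their only sample-size figure is the power behind n = 57. Sum Bin(k₁; 38, 0.49) × Bin(k₂; 19, 0.16) over all outcomes where P[Beta(k₁+1, 39−k₁) > Beta(k₂+1, 20−k₂)] > 0.90. The result is 0.910, which reproduces the stated power of at least 90%.

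**2. Chance entries by arithmetic.** Inputs: m = 15 or 14 candidates and entry at 0.2 (SAP 4.4.5). Treating candidates as independent and null:
- Expected entries = m × 0.2: 15 × 0.2 = 3.0; 14 × 0.2 = 2.8.
- P(at least one) = 1 − 0.8^m: 0.965 for 15; 0.956 for 14.

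**3. Simulation of the forward selection.** n = 57 (38:19), 15 candidates, 3000–4000 runs per row. The documents give no predictor distributions or effects, so these are assumed: EASI, BSA and vIGA-AD correlated, and age equal to onset plus duration apart from rounding, except in the first row, where all candidates are independent. Treatment effects (d) and prognostic effects are in SD units. In the two rows with no real effect, treatment itself counts as null.

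| Real effects assumed | Mean number selected | Mean null entries | Runs with ≥1 null entry | Null share of selected | Treatment enters |
|---|---|---|---|---|---|
| None, independent | 3.21 | 3.21 | 97% | 100% | 21% |
| None, correlated | 2.95 | 2.95 | 95% | 100% | 22% |
| Treatment 0.2 | 3.06 | 2.75 | 94% | 90% | 32% |
| Treatment 0.5 | 3.40 | 2.75 | 95% | 81% | 65% |
| Treatment 0.8 | 3.65 | 2.73 | 94% | 75% | 92% |
| Treatment 1.0 | 3.69 | 2.72 | 94% | 74% | 98% |
| Treatment 0.5 + 2 factors at 0.3 | 4.49 | 2.39 | 92% | 53% | 64% |
| Treatment 0.8 + 3 factors at 0.4 | 5.79 | 2.18 | 90% | 38% | 90% |
| Treatment 0.8 + 5 factors at 0.4 | 7.19 | 1.80 | 86% | 25% | 88% |

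With nothing real, the selected model still shows an apparent R² of 0.16–0.18.

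**4. Treatment failing to enter.** The planning rates of 0.49 and 0.16 correspond, on a normal latent scale, to d = Φ⁻¹(0.49) − Φ⁻¹(0.16) = 0.97. For treatment tested alone, the non-centrality is d × √(38 × 19/57) = 3.56d on 55 degrees of freedom. P(p ≤ 0.2) is then 0.984 at d = 0.97 and 0.687 at d = 0.5. In the full procedure, treatment is absent in about 2% of runs at d = 1.0 (1 − 0.977), 35% at 0.5 (1 − 0.654) and 68% at 0.2 (1 − 0.318).

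**5. The three time variables.** If onset is taken from the diagnosis date, onset plus duration equals age apart from rounding. Median variance inflation factors for the three together are then about 550–1100. With a mean onset-to-diagnosis gap of 3 years (assumed) they are 17–35, and with 5 years 7–14. In the correlated scenarios, however, two or more of the three enter together in only about 2–3% of runs, and all three in about 0.5%. The consequence is an arbitrary pick of one, not a model made unstable by all three.

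**The case against.** The strongest reply is that this is an openly exploratory analysis. It sits in a section on descriptive statistics, its lenient threshold is stated, and no decision rule uses the output. Pre-specified subgroup summaries (SAP 4.6.2) cover many of the same factors. Randomisation also makes baseline factors roughly unrelated to arm, so omitting treatment mainly adds residual variance and does little to bias which factors are chosen. All of that stands, and it keeps the point small. It does not settle the matter, because the section promises to identify a set and the procedure cannot support that reading unaided.

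Several stronger readings are tempting but not supported:
- *Treatment can be dropped.* There is no removal step; it can only fail to enter, and rarely does near the planning effect.
- *The set will be mostly noise.* That depends on how many factors are truly prognostic. The null share is 53–100% with none to two real factors but 25–38% with three to five moderate ones. The documents do not say which case applies.
- *Collinearity wrecks the model.* The very large variance inflation factors need all three time variables in one model and onset equal to diagnosis. The first is rare and the second is not established, since SAP 4.1.1 uses two different terms.
- *IgE is entered untransformed.* SAP 4.4.5 states no scale, so this is inference from silence.
- *The result will steer the next trial's population.* The documents do not say so, and the models contain no treatment interactions.

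**Conclusion.** The point holds as a cheap improvement to an exploratory analysis. With entry at p ≤ 0.2 and 14–15 candidates, about three variables are expected by chance if no baseline factor is prognostic. At least one null factor entered in 86–97% of runs in every scenario examined. The selected set should not be called most influential on this evidence alone.

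Treatment is not guaranteed a place: it is absent in about 2% of runs near the planning effect and about 35% at d = 0.5. The SAP's introductory wording, which names treatment beside the baseline characteristics as predictors, might be read as always including it. The list and the empty starting model say otherwise, so clarification is needed at the least. The choice among age, duration and age of onset is arbitrary.

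The expected count follows from the SAP's threshold and number of candidates. The simulated percentages rest on assumed distributions, correlations and effects, and the planning d rests on a latent-normal conversion of the two response rates. The primary conclusion does not depend on any of this.

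**What to change.** In SAP 4.4.5:
1. Force treatment into every univariate and multiple model, consistent with SAP 4.3.2 and 4.4.2.
2. Offer only two of age, disease duration and age of onset, and state where year of onset comes from. Little is lost, because any two nearly determine the third.
3. Report bootstrap selection frequencies for every factor beside the selected model.
4. State under the table that about three chance entries are expected at p ≤ 0.2 when nothing has an effect.

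Items 1 and 2 do not cure the chance selection. With 13 candidates left, 13 × 0.2 = 2.6 null entries are still expected and 1 − 0.8¹³ = 0.945. The threshold drives this: at 0.05 the figures would be 13 × 0.05 = 0.65 and 1 − 0.95¹³ = 0.487. Items 3 and 4 do not lower the count either, but they let a reader see how stable each selection is. Null factors will also be chosen in some resamples, so the frequencies need that caution. Replacing forward selection with ridge or lasso is a preference of method and not required.

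The cost is a few sentences, a little extra code and a more cautious reading of the output. No new data are needed beyond stating the source of the onset year.
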